# **Protocol Summary**

**Title**: Metagenomic Studies of MRSA Colonization - Nose, Throat, and Skin Cultures before and after use of Antibacterial Nasal Ointment and Antibacterial Soap for Showering in Adults who live in the Community and have Current *S. aureus* Colonization

**Population**: Approximately 250 male and female adults with *S. aureus* colonization at enrollment from a single geographic location in the US to achieve a final sample size of at least 40.

Site: Baltimore VA Medical Center

[figure not shown]
Study Duration: Approximately 18 months

#### Duration of Participant's Participation: Up to 52 weeks

#### **Objectives:**

- To collect specimens from multiple body sites in a non-invasive manner to serve as sources of measurement of the core microbiomes associated with the anterior nares, posterior pharynx, skin over the right subclavian vein and the right femoral vein and perirectal skin (the skin around the anus), in *S. aureus* colonized adults
- To collect specimens from multiple body sites in a non-invasive manner to serve as sources of measurement of the change in the core microbiomes associated with the anterior nares, posterior pharynx and skin over the right subclavian vein and the right femoral vein and the perirectal skin in response to application of a nasal and skin *S. aureus* decolonization regimen in *S. aureus* colonized adults
- To collect serum from the participants to examine immune responses to organisms that are identified in the microbiome
- To collect blood from the participants to examine the relationship of host genotype (by either genotyping or sequencing the DNA) to organisms that are identified in the microbiome present on/in an individual

# 1 Schematic of Study Design

# 2 Background Information and Rationale

### 2.1 Background Information

**Our adult bodies harbor** ~10 times more microbial cells than human cells. Collectively they are known as the human microbiome. A significant number of these microbes are difficult to grow in culture leading to inherent biases in the use of culture based methods to describe it. Our microbiome carries out many metabolic reactions not encoded for in the human genome and are necessary for our health. The NIH funded Human Microbiome Project (HMP) was developed to "to understand the microbial components of the human genetic and metabolic landscape and how they contribute to normal physiology and predisposition to disease" (1). The HMP's focus is on characterizing the microbiome of the gastrointestinal tract, the oropharynx, the anterior nares, the vagina and the skin in young healthy adults.

Staphylococcus aureus (SA) is a part of the human microbiome and an important cause of both community and hospital acquired infections. Methicillin-resistant *S. aureus* (MRSA) is a type of *S. aureus* which is resistant to penicillin-like antibiotics, but susceptible to other antibiotics. *S. aureus* which are not methicillin resistant is referred to as methicillin-susceptible *S. aureus* (MSSA). *S. aureus* is a normal part of the human microbiome. Colonization is frequently prolonged (6) and patients are at risk for infection when the opportunity (e.g. central line or surgery) occurs. Patients with *S. aureus* colonization serve as the source of transmission to others thus preventing transmission decreases infections by reducing the number of patients who serve as a source of transmission. Efforts to decolonize patients with *S. aureus* colonization have not been successful in the long-term (7).

#### Hospital infection control programs strive to prevent S. aureus (and other) infections

promoting: hand hygiene, isolation for patients infected or colonized with multi-drug resistant organisms such as MRSA and practices that decrease the risk of specific infections such as maximal barrier precautions during central line placement. Recently forces external to individual hospitals have increased the pressure to prevent infections (8). Medicare will no longer reimburse for certain healthcare associated infections. Many states have made healthcare associated infections publicly reportable (9). In addition, some states (and the national VHA) have legislatively mandated MRSA screening with surveillance cultures (10). This has lead to the growing use of less well established infection control practices including *S. aureus* decolonization.

"Decolonization" is a controversial and rapidly growing strategy to prevent *S. aureus* and other healthcare associated infections. The goal of decolonization is to prevent *S. aureus* infections in the decolonized patients as well as reduce the risk of *S. aureus* transmission to other patients. Decolonization involves the application of targeted or non-targeted antimicrobials to the skin and mucosal surfaces. Two commonly used agents for *S. aureus* decolonization are mupirocin and chlorhexidine.

Mupirocin is an agent with bactericidal activity against Gram-positive bacteria produced by fermentation using the organism *Pseudomonas fluorescens*. It is most commonly applied intranasally and is only available by prescription. Two recent meta-analyses concluded that mupirocin decreased *S. aureus* infections in *S. aureus* colonized surgical patients (7, 11).

Intranasal mupirocin is increasingly being used to treat methicillin-resistant *S. aureus* (MRSA) colonization which is detected on mandated surveillance cultures (12). Even more recently a combination of MPC and CHX was shown to decrease surgical site infections due to *S. aureus* (MRSA or MSSA) (13).

Chlorhexidine is a broad spectrum antiseptic agent with activity against Gram-positive and negative bacteria as well as fungi. It is available as a topical solution ranging in concentration from 0.5% to 4% without a prescription. Chlorhexidine is used in intensive care units (ICU's) to prevent central line associated blood stream infections (14). Chlorhexidine baths have also been shown to decrease MRSA and VRE acquisition in the ICU setting (15). Chlorhexidine was recently shown to be superior to Povidone-Iodine for surgical site antisepsis (16).

### 2.2 Rationale

Given the role of our normal flora in serving as a barrier to colonization with more pathogenic organisms (aka colonization pressure), decolonization regimens may have unintended negative consequences. For example, preliminary 16S rRNA data suggest that Gram-negative bacilli from the orders Enterobacteriales and Pseudomonadales are present as a component of the human microbiome of the anterior nares. Decolonization with intranasal mupirocin, a Gram-positive antimicrobial agent, may increase this Gram-negative colonization and consequently increase the likelihood of infections due to these pathogens. The recent Cochrane Review of Mupirocin ointment for Preventing S. aureus infections in nasal carriers concluded that the use of mupirocin led to a relative increase in infections due to bacteria other than S. aureus (Analysis 6.1: RR 1.4 95%CI 1.1-1.7) and that infections due to Gram-negative bacilli were increased but not statistically significant (Analysis 6.3: RR 1.7 95%CI 0.8-3.5)(7). Although suggestive, these analyses are limited in scope because few of the mupirocin clinical trials have reported overall infections. Many, including the recent NEJM paper, have just focused on S. aureus infections (13). Furthermore these trials have not looked at the impact of mupirocin on colonization with other organisms. If mupirocin promotes colonization with Gram-negative bacilli, this is an important adverse event given that colonization with Gram-negative bacilli increases the risk of Gram-negative bacilli infection in hospitalized patients (17-19) and the increasing antibiotic resistance in the Enterobacteriaceae, Pseudomonas and Acinetobacter over the past decade (20). Our short term goal is to determine if these increasingly used decolonization regimens, targeted at controlling MRSA in particular, may result in a secondary negative effect of promoting colonization with pathogenic Gram-negative bacilli. This could be an unintended consequence of healthcare policies which are indirectly promoting the use of these decolonization regimens and would have an impact of the use of mupirocin for infection control purposes. The long term goal of this research is to use the information gained to develop new ways to manipulate the human microbiome to reduce the risk of S. aureus infections with minimized negative consequences.

### 2.3 Risk/Benefits

The risks of the proposed study are minimal. There are possible risks and discomforts from this study for participants.

BACTROBAN NASAL (mupirocin calcium ointment, 2%) is a licensed, widely used, and generally well tolerated topical antibiotic available by prescription. Reported side effects noted in the packet insert include: Headache, 9%; Rhinitis, 6%; Respiratory disorder, including

upper respiratory tract congestion, 5%; Pharyngitis, 4%; Taste perversion, 3%; Burning/stinging, 2%; Cough, 2% and Pruritus, 1%.

Antimicrobial antiseptic skin cleanser (4% chlorhexidine), is an FDA- approved formulation and application for topical 4% chlorhexidine, an antiseptic solution which is available without a prescription. It is widely used for pre-operative skin cleansing and extremely well tolerated. Mild skin irritation can occur.

The sampling methods for the anterior nares, throat, skin, and perirectal skin sites is physically non-invasive, but there could some discomfort during the procedure. The potential discomfort from obtaining the specimens does not place any participant at physical risk. While taking the throat culture, the participant may gag and possibly vomit. A trained research coordinator will use very gentle pressure while performing the cultures to minimize these risks. However, there is the possibility of psychological discomfort from the specimen collection.

The drawing of blood may cause brief discomfort or slight pain and, rarely, fainting. Bruising at the site of the blood draw may occur but can be prevented or lessened by applying pressure for several minutes. Infection at the site where blood is drawn is not likely, and this risk will be minimized by the use of alcohol swabs and sterile gauze.

There is a risk that health information could be in accidentally disclosed to others outside the study. Confidentiality will be protected to the fullest extent permitted by law. Despite the recent passage of a federal law that bars genetic discrimination in employment and some types of insurance, the use by others of genetic information from the eventual study of the blood specimens could conceivably impact the participant negatively in some way. For example, there is a very small risk that genetic information obtained by this study could be used by law enforcement officials to try to learn more about the participants or their family members for the purpose of a criminal investigation.

There may be adverse events that are not yet known. For example, we are studying whether mupirocin leads to an increase in Gram-negative colonization in the anterior nares and throat which might lead to an increased risk of Gram-negative infections. To date, there is evidence that mupirocin leads to an increase in the relative risk of infections due to organisms other than *S. aureus* including Gram-negative bacilli (7); however, this was in surgical and dialysis patients, a group at increased risk for infections in genera and was not associated with an absolute risk of infectionl. In general, Gram-negative bacilli are opportunistic pathogens. They colonize frequently, but infrequently cause infection. To minimize the risk of infection, we are excluding older adults who would be at increased risk of infection (e.g. surgical and dialysis patients, those with recent hospitalizations, history of urinary tract infections).

There is no alternative treatment or procedure to participating in this study, but individuals have the right to decline participation in this research without any risk.

There are no direct benefits to study participants. Participants will receive a regimen that will eradicate *S. aureus* colonization in the short term. Although *S. aureus* colonization contributes to the risk of *S. aureus* infection, the absolute risk of *S. aureus* infection is small enough that this is not believed to be a direct benefit. This study will contribute knowledge about the human microbiome. *S. aureus* and other opportunistic pathogens are members of this

January 9, 2020

microbiome. When the opportunity arises (e.g. a person has surgery or a central venous catheter), these bacteria can cause an infection particularly in hospitalized patients. Understanding the human microbiome in *S. aureus* colonized participants can help us develop new ways to prevent *S. aureus* infections.

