### 5.2 Inclusion Criteria

- Adults living independently in the Baltimore area
- Willing and able to provide anterior nares, throat, skin, and perirectal specimens over up to an 18 week time period.
- Willing and able to administer intranasal mupirocin and topical chlorhexidine over a five day period.
- Capable of understanding and complying with the entire study protocol.
- Provided signed and dated informed consent.
- *S. aureus* colonization on at least one of the enrollment cultures (after informed consent)

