### 5.3 Exclusion Criteria

- Use of anticancer chemotherapy or radiation therapy (cytotoxic) within the past 6 months
- History of HIV infection with most recent CD4 of <200
- Immunosuppression medications within the past 3 months
- Use of systemic antibacterial or antifungal agents in the past 3 months
- Use of nasal steroids currently or in the past 3 months
- Use of nasal antimicrobial ointment in the past 3 months
- Any current indwelling percutaneous medical device or urinary catheter
- Acute care hospitalization in the past 3 months
- Planned surgery or hospitalization during the study period

- History of an allergic reaction to chlorhexidine or mupirocin
- Oral temperature of >100 F at enrollment visit
- BMI <18 or >35 at enrollment visit

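### Section 2.3 names dialysis patients and people with a history of urinary tract infection as excluded for safety, but the section 5.3 criteria cover these two groups only in part

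*Protocol*

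**What the plan says.** Section 2.3 (Risk/Benefits) of the protocol raises the possibility that mupirocin increases Gram-negative colonization and, through it, infection. It notes that the evidence for more infections with organisms other than S. aureus comes from a different kind of patient: "this was in surgical and dialysis patients, a group at increased risk for infections". It then describes the safeguard in the present tense: "To minimize the risk of infection, we are excluding older adults who would be at increased risk of infection". The examples in brackets are "e.g. surgical and dialysis patients, those with recent hospitalizations, history of urinary tract infections".

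Section 5.3 (Exclusion Criteria) lists 12 criteria. Those closest to the four examples are:

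- "Acute care hospitalization in the past 3 months"
- "Planned surgery or hospitalization during the study period"
- "Any current indwelling percutaneous medical device or urinary catheter"
- "Use of systemic antibacterial or antifungal agents in the past 3 months"

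No criterion in section 5.3 mentions dialysis, renal disease or urinary tract infection. The inclusion criteria in section 5.2 open with "Adults living independently in the Baltimore area" and contain nothing that would remove either group.

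**The concern.** Section 2.3 sets the cited evidence of harm apart from this study on the ground that it came from surgical and dialysis patients, and then says such patients are being excluded. For dialysis patients, that reassurance needs an exclusion that section 5.3 does not list. The same gap exists for people with a history of urinary tract infection.

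The eligibility criteria are what staff apply. Section 5.1 has the coordinator review them before the enrollment visit is booked, and section 8.1 has participants screened against them on Day 0. A medical history is taken at that visit, but no rule directs staff to exclude anyone because of dialysis or a past urinary tract infection. A site following the criteria exactly could therefore enroll and treat a person whom the risk section describes as excluded. The IRB reading section 2.3 would have been told of a safeguard wider than the one in force.

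**Working it through.** No formula applies. The check compares each group named in section 2.3 with every rule that could keep a person out: sections 5.2, 5.3 and 5.4, and the screening steps in section 8.1.

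| Group named in section 2.3 | Nearest criterion in section 5.3 | Cover |
|---|---|---|
| Surgical patients | Planned surgery or hospitalization during the study | Matched, as planned surgery |
| Recently hospitalized | Acute care hospitalization, past 3 months | Matched, with a 3-month window |
| Dialysis patients | Indwelling percutaneous device or urinary catheter | Partial: only dialysis through such a device |
| History of urinary tract infection | Systemic antibacterial use, past 3 months; current urinary catheter | Partial: only recently treated infection, or a person with a catheter now |

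**Count.** Of the 4 named groups, 2 have a matching criterion and 4 − 2 = 2 do not.

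**Who passes.** Two kinds of person meet no exclusion on these grounds:

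- a dialysis patient without an indwelling percutaneous device;
- a person whose urinary tract infection was treated more than 3 months before enrollment, since a history of infection carries no time limit in section 2.3 while the antibacterial criterion reaches back 3 months.

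**Other rules.** Section 5.2 requires independent living, willingness to give specimens and self-administer the regimen, capacity, consent and a positive culture. None of these removes either group. Section 5.4 withdraws people found to have been ineligible, which leads back to the same criteria. It also withdraws those unable to follow the regimen and those with negative cultures. Section 8.1 screens on the inclusion and exclusion criteria and adds no further condition.

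**Why dialysis matters most.** Section 2.2 cites a relative risk of 1.4 (95% CI 1.1-1.7) for infections with bacteria other than S. aureus, and 1.7 (0.8-3.5, not statistically significant) for Gram-negative infections. Section 2.3 says the increase was seen in surgical and dialysis patients. So one of the two incompletely covered groups belongs to the population behind the cited signal.

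**Size.** Section 11.3 assumes 250 enrolled and about one in five colonized, which gives 250 × 1/5 = 50 people who could go on to treatment. The protocol does not say what share of them would be on dialysis or have had a urinary tract infection, so no count can be given. Exposure is plausible, because section 5.1 recruits from VA clinics and from VA records of patients with S. aureus cultures in the last three years.

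**The case against.** The strongest reply is that the list in section 2.3 is only illustrative and that the criteria already keep out many people at raised risk. Much of this is true. Recent hospitalization and planned surgery are excluded. The device, catheter and antibacterial criteria remove some dialysis patients and some people with urinary tract infection. Section 5.3 also excludes recent cytotoxic therapy, immunosuppressive medication, HIV infection with a low CD4 count, and fever at enrollment. A reader might infer from the two missing criteria that the mitigation does not operate at all; the documents do not support that. But examples of people said to be excluded should themselves be excluded, and two of the four are excluded only in part.

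A reader might also infer that the minimal-risk argument rests on these exclusions. It does not. Section 9 ties minimal risk to the specimen collection methods. Section 2.3 relies as well on the products being licensed or FDA-approved and well tolerated, and on Gram-negative bacilli colonizing often but seldom causing infection.

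A third tempting inference is that enrolling these groups would cost data through antibiotic use. Nothing in the protocol quantifies this. Section 5.5 keeps such participants in follow-up and drops only their post-antibiotic data from the primary analysis, and section 11.3 already allows for 10 participants lost to hospitalization or antibiotics.

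Finally, the safeguard sentence speaks of older adults, although sections 5.2 and 5.3 set no age limit beyond adulthood. This suggests that the sentence may not have been written with these criteria in view, so a drafting error in section 2.3 is as plausible as an omission from section 5.3. It does not remove the conflict, since neither condition is an exclusion at any age.

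**Conclusion.** The point holds as an internal contradiction on a participant-safety safeguard. For two of the four groups that section 2.3 gives as excluded, section 5.3 provides only incidental, partial cover, so the plan as written allows enrollment and treatment of people it says are kept out. This is more than a clerical matter because it concerns who is exposed to a risk that the protocol itself identifies. It does not touch any endpoint, analysis or sample-size figure.

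The conclusion rests on the protocol text alone and assumes that no eligibility rule outside the sections shown names either condition. The procedures and forms to which the protocol refers were not available. The documents do not settle which of the two sections reflects the intended rule.

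**What to change.** Reconcile sections 2.3 and 5.3 so that the stated mitigation and the eligibility criteria describe the same population. The investigators and the IRB should decide which section changes. The reference to older adults in section 2.3 should be settled in the same amendment, as should any other study document that repeats the statement. Then check any participants already enrolled against the agreed list and put anyone affected before the IRB.

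The cost is a short amendment and a record check. If section 5.3 is the one to change, screening gains the corresponding questions and probably a few more screen failures. If section 2.3 is the one to change, the IRB needs to look again at the risk statement with the narrower safeguard in view. No analysis needs to be rerun or redesigned.

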### 2.4 Study Conduct

This study will be conducted in compliance with the protocol approved by the UMB Institutional Review Board (hereafter referred to as IRB) and VAMHCS R&D Committee and according to Good Clinical Practice standards and the VHA Handbook 1200.05 Requirements for the Protection of Human Subjects in Research. No deviation from the protocol will be knowingly implemented without the prior review and approval of the IRB except where it may be necessary to eliminate an immediate hazard to a research participant. In such case, the deviation will be reported to the IRB as soon as possible.

### 3 Study Objectives

This is a mechanistic patient-oriented research study designed to characterize the baseline microbiome of body sites associated with *S. aureus* colonization and to understand the effect of a local decolonization regimen on the microbiome of the nose, throat and three skin sites in *S. aureus* colonized adults.

There are two additional objectives. The first is to determine the immune responses to organisms that are identified in the microbiome. Specifically, this objective will assess whether participants with successful decolonization of *S. aureus* colonization have higher *S. aureus* specific antibody levels than participants without successful decolonization of *S. aureus* colonization. Other responses to other bacteria may be looked at in future studies. The second is to examine the relationship of host genotype (by either genotyping or sequencing the DNA) to the microbiota present on/in an individual. Specifically, this objective will assess whether participants with successful eradication of *S. aureus* colonization have a different genotype than participants without successful eradication of *S. aureus* colonization.

